9.1.4 CDS QUALITY ASSURANCE AND TESTING

Additional quality assurance (QA) and testing will be conducted to ensure appropriate functioning of the algorithms, which determine clinical recommendations made by the CDS to the provider and patient. Study personnel at EH will be responsible for manual chart review of select patients' electronic medical records. No information will be will collected, used, or disclosed for study analyses.

A full waiver of HIPAA Authorization is requested to access medical record for QA and testing purposes.

9.1.5 DATA HANDLING AND RECORD KEEPING

9.1.5.1 DATA COLLECTION AND MANAGEMENT

Data from the PedsBP CDS will be stored throughout the study, to be linked through a unique study ID with the minimum EHR and administrative data to evaluate study outcomes. Data transfer is secured using certificate-based authentication and IP whitelisting. In addition, data access is secured using FHIR based OAuth protocols.

In compliance with HIPAA regulations¹⁴⁰, no personally identifiable health information (PHI) will be shared outside of the affiliated covered entities (ACE).

The study team has extensive experience in health services research and clinical research with human subjects, with procedures to safeguard privacy and personal information. All study records are protected by:

- Locked storing all paper records in a secure location
- Use of untraceable study ID numbers instead of names wherever possible
- Password protection as well as firewalls
- Strong user login authentication on all electronic devices
- Physical security for all electronic devices containing personal information

We will establish common study variable definitions drawn from national standards and from definitions used in HP's previous studies.¹⁰¹ We will construct variable definitions and data-extraction procedures for demographics, enrollment characteristics, vital signs, pharmacy, and outpatient encounters and diagnoses. We will develop conceptual and operational definitions and technical specifications for data elements without established definitions. Data from all sources will be restructured into a common format and data elements combined into uniform files. All person-level information will be linked by a unique identifier so data can be compiled to the person level. Data integrity will be assessed to ensure that observations are valid, reliable, and consistent. Each variable will be tested for completeness and out-of-range values. The accuracy of HTN identification,¹⁰² selected laboratory results, BP data, and pharmacy data¹⁰³ has been established in previous work in adult cohorts and found to be excellent. Definitions will be adapted from HP's prior Peds & TeenBP clinical trial.²²⁻²⁴

9.1.5.2 STUDY RECORDS RETENTION

Data will be retained in secure storage following the completion of the study in accordance with Minnesota and federal law. We guard against the potential for breach of subject confidentiality through a multi-layered system of data protection policies, processes, staff training, software safeguards and physical security measures for both paper and electronic data involved in research.

The following measures will be taken to protect subjects from the risk of breach of confidentiality:

- All data collected in the study will be identified by using a previously assigned arbitrary and unique subject identification number to each participant.
- A file containing a link between the study ID and individually identifying information will be maintained by a EH programmer who is member of the study team through the conclusion of the study.
- A crosswalk table linking the study ID to a patient identity will be destroyed within 12 months after the linked databases needed to test study hypotheses are completed.
- All electronic study data will be maintained in a computerized database residing on a username- and password-protected file server to which only the researchers involved in the study will have access.

- All study-related paper documents containing individually identifiable information will be maintained in locked file cabinets.

9.1.6 PUBLICATION AND DATA SHARING PLAN

In addition to presenting results at national meetings and in peer-reviewed journals, the investigators are available for any other dissemination activities that AHRQ staff deem appropriate. We plan to register this study on ClinicalTrials.gov and post results of the study on ClinicalTrials.gov when available, consistent with HP and EH research policies. As study findings become available, we will share with EH clinical leaders and EH Patient Advisory Councils. The importance of translating evidence-based care recommendations into primary care practice has long been known as a very high priority but few projects have addressed this need in children and adolescents living in rural regions, at risk of long-term adverse cardiovascular outcomes by virtue of elevated BP and related cardiovascular risk factors and with limited access to pediatric subspecialty care. A key deliverable of this project is identification of optimal implementation strategies for clinical decision support or other care improvement interventions in rural clinics. These findings can then be extended to improve care for other pediatric risk factors and clinical conditions, especially in rural areas. The proposed study aims to translate the billions of dollars of private and public-sector investment in EHR technology into tangible improvements in the quality of care that children and adolescents receive in primary care practices.

Sharing of study procedures and outcomes is an essential element of this research. We are determined to ensure that data sharing occurs on a local, regional and national level.

Our plan includes the following:

Local: We will work closely with clinical and administrative leaders at Essentia Health (EH) to ensure our CDS tool will be well accepted and locally relevant. During the intervention and analysis phases of the project we will continue to meet with these leaders to update them on our findings. If desired, once the intervention period is complete, we will activate the CDS at all EH pediatric and family practice clinical sites. Findings of our research will be presented to local clinical and administrative leaders.

Regional: To assure regional dissemination of results and findings of this research will be presented at regional conferences, such as the Minnesota Academy of Family Physicians Innovation and Research Forum, and others. Results will also be communicated to other regional and state-wide medical groups including the Minnesota Department of Health and the Institute for Clinical Systems Improvement, a regional shared learning quality improvement organization.

National: Our main study findings will be presented at national meetings and will be published in peer-reviewed journals. If the funding agency so desires, and if permitted under then-current law, at the conclusion of the funding period we may provide a de-identified data set to AHRQ at their written request for the use of other qualified researchers in the future.

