Study Population:	To participate in this study, primary care providers must practice at one of the participating EH clinics and meet these additional eligibility criteria: (a) be a pediatric or family medicine care provider (pediatrician, family physician, nurse practitioner or physician assistant), and (b) provide ongoing clinical care for children and adolescents. Patients enrolled will be 6-17 years with BP, height and weight recorded. We estimate patients will have an average of 2.02 visits per patient over the study period. Similar to demographics of the region, the population is 90% white, non-Hispanic.

Description of Sites/Facilities Enrolling Participants:	Pilot - Two Essentia Health primary care clinics CDS control & intervention - up to 45 Essentia Health primary care clinics
Description of Study Intervention/Experimental Manipulation:	Up to 45 community-based, Essentia Health primary care clinics with the largest number of visits among youth 6-17 years will be balanced and randomly allocated in a 1:1:1 allocation ratio to usual care, low-intensity implementation, or high-intensity implementation of the PedsBP CDS.
Study Duration:	Pilot testing and interviews: January 2022 – June 2022 18-month CDS intervention period: August 2022 – January 2024 (anticipated) 12-month CDS follow-up period: February 2024 – January 2025 Survey clinicians and rooming: October 2023 – December 2023
Participant Duration:	Pilot interviews of clinicians and staff – April 2022 – June 2022 Data collection for study-eligible adolescent patients – August 1, 2022 – July 31, 2025 Surveys of clinicians and staff – October 2023 – December 2023

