1.3 SCHEDULE OF ACTIVITIES

IRB Submission-Related Activities

Phase 1 Study Aspect	Estimated Start Date	Completion Date	Recruitment / Authorization	Consent / Assent	IRB Submission for Approval
Development, quality assurance and testing of the CDS	July 2021	End of Study	Full waiver of HIPAA authorization	Requesting waiver of consent and assent	Submitted initial submission 10/12/20 and amendment 04/28/21
Pilot clinics - PedsBP CDS implementation, operation, quality assurance and testing (see section 9.1.4)	Jan 2022	End of Study	Full waiver of HIPAA authorization	Requesting waiver of consent and assent	Submitted amendment 01/07/22
Interview pilot clinicians and rooming staff	Jan 2022	June 2022	Contact by mail, email or in-person	Informed consent	Submitted amendment 03/16/22
Phase 2 Study Aspect	Estimated Start	Completion Date	Recruitment / Authorization	Consent / Assent	IRB Submission for Approval
Intervention - CDS implementation, operation, testing and data collection in up to 45 study clinics	Aug 2022	Jan 2025	Full waiver of HIPAA authorization	Requesting waiver of consent and assent	Submitted amendment 08/16/22
Post-Implementation rooming staff and PCP surveys	Oct 2023	Dec 2023	Contact by mail/email	Requesting waiver of informed consent documentation	Submitted amendment 10/09/23

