4.1.3 PHASE 3 – ANALYSES

This period encompasses analyses, reporting of key study results, and implementation of the intervention in the non-intervention clinics, if requested by EH. Throughout the study, there will be ongoing analysis of data as they become available, and preliminary results will be presented at meetings and/or reported in peer-reviewed articles.

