5.1 INCLUSION CRITERIA

Patients will be eligible for the PedsBP CDS tool if:

- a) 6-17 years of age
- b) BP measured and entered in the vital sign section during an ambulatory primary care visit in a randomized primary care clinic
- c) not pregnant or postpartum

Patients must meet these eligibility criteria to be included into study analyses:

- a) have at least one index visit to a randomized primary care clinic in the intervention period
- b) meet eligibility for PedsBP CDS at index visit
- c) no previous HTN diagnosis prior to index visit
- d) not taking antihypertensive medication prior to index visit
- e) not opted out of use of their data for research via general consent prior to performing analyses

Primary care providers must meet these eligibility criteria to participate in this study:

- a) practice at a randomized primary care clinic
- b) be a pediatric or family medicine care provider (pediatrician, family physician, nurse practitioner or physician assistant), and
- c) provide ongoing clinical care for children and adolescents

Provider and rooming staff inclusion criteria for interviews and surveys are provided in separate protocols.

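### Section 9.1.6 allows the CDS to be switched on at usual-care clinics while some 6-month H3 windows are still open; the likely dilution of H3 is small

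*Combined protocol and SAP*

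**What the plan says.** **Roll-out.** Section 9.1.6 (Local) states: "If desired, once the intervention period is complete, we will activate the CDS at all EH pediatric and family practice clinical sites". The sentence just before it has a wider time frame: "During the intervention and analysis phases of the project we will continue to meet with these leaders". Section 4.1.3 puts roll-out in Phase 3, described as "implementation of the intervention in the non-intervention clinics, if requested by EH", with no date.

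**Calendar.** The synopsis (1.1, Study Duration) gives "18-month CDS intervention period: August 2022 – January 2024", marked as anticipated, and then separately "12-month CDS follow-up period: February 2024 – January 2025". Under Participant Duration it gives an end of patient data collection of July 31, 2025. The schedule (1.3) has one Phase 2 row, "Intervention - CDS implementation, operation, testing and data collection in up to 45 study clinics", running from August 2022 to January 2025.

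**Outcome windows.** To be analysed, a patient must "have at least one index visit to a randomized primary care clinic in the intervention period" (5.1). Section 8.3 scores the Aim 2 outcomes over 6 months from meeting HTN criteria, and scores patients with no follow-up visit on what was done at the index visit. BP control is assessed at 12 months. The synopsis and 6.1.1 fix each patient's arm by the clinic of the index visit. Section 8.4 does not mention recognition that occurs after a usual-care clinic has received the CDS.

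**The concern.** The permission in 9.1.6 starts when the intervention period ends. The H3 windows of patients who qualify in the last 6 months of that period close up to 6 months later. If a usual-care clinic were activated in between, a patient returning with a high BP could be recognised because of the CDS and would be counted as a usual-care success. That raises the usual-care rate and shrinks the H3 contrast, one of the two primary comparisons with usual care. The 6-month management outcomes and the exploratory 12-month BP comparison have the same exposure. H1 and H2 are same-visit outcomes and H4 does not use the usual-care arm, so none of these is affected.

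What is at stake is how to read a weak or null H3 result. Without a stated activation date, a reader cannot confirm that the comparator remained usual care throughout follow-up.

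**Working it through.** **1. Reproduce the plan's H3 power (8.2).** Inputs: 1,060 patients, 45 clinics (15 usual care, 30 CDS), ICC 0.035, two-sided alpha 0.05.
- Patients per clinic: m = 1,060/45 = 23.56. Design effect: 1 + (23.56 − 1) × 0.035 = 1.789.
- Usual care: 1,060/3 = 353 patients (equal clinic sizes assumed). CDS arms: 707.
- SE = √{1.789 × [p₁(1−p₁)/353 + p₂(1−p₂)/707]}; power from a noncentral t with 43 df.
- 20% vs 37%: SE 0.0374, power 0.993. The plan says 99%.
- 20% vs 31%: SE 0.0368, power 0.833. The plan gives 11 points as the minimum detectable difference at 80% power. Two other standard formulas put the exact 80% difference at 10.6 to 10.9 points, which rounds to 11.

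**2. Open windows at the end of the intervention period.** Uniform accrual is assumed.
- 18-month period: 6/18 = 33%, so 353 × 0.333 = 118 patients. On the anticipated calendar the last window closes in July 2024.
- 24-month period: 6/24 = 25%, about 88 patients. A July 31, 2025 end of data collection, less 12 months of follow-up, would fit such a period, but the documents do not state it.
- If accrual falls linearly to zero at month 18: (6/18)² = 11%, about 39 patients.
- 12-month BP windows: 12/18 = 67% open.

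**3. How many return in the remaining window.** Time left is uniform on 0 to 6 months. At a return rate r per month, the mean fraction returning is f = 1 − (1 − e^(−6r))/(6r). The documents give no rate for this group, so four assumed rates are used:
- 50% with a follow-up BP in 12 months in usual care (8.4.1): r = ln 2/12 = 0.0578.
- 2.02 visits per patient (1.1) less the index visit, over 18 months: r = 1.02/18 = 0.0567.
- Zero-truncated Poisson with mean 2.02 (λ = 1.62): r = 1.62/18 = 0.0900.
- The same 1.02 later visits over an average of 9 remaining months: r = 1.02/9 = 0.1133.

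**4. Effect on H3.** 18-month period; every returning patient gains the full CDS effect. Share exposed s = f/3; remaining difference = planned difference × (1 − s).

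| r | f | Patients (118 × f) | s | 17 points becomes (power) | 11 points becomes (power) |
|---|---|---|---|---|---|
| 0.0567 | 0.152 | 18 | 5.1% | 16.1 (0.99) | 10.4 (0.79) |
| 0.0578 | 0.155 | 18 | 5.2% | 16.1 (0.99) | 10.4 (0.79) |
| 0.0900 | 0.227 | 27 | 7.6% | 15.7 (0.98) | 10.2 (0.76) |
| 0.1133 | 0.274 | 32 | 9.1% | 15.4 (0.98) | 10.0 (0.75) |

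Full uplift for every returning patient is generous. The tailored advice needs a BP at or above threshold (6.1.1, sixth component), patients already recognised cannot gain, and actions at the qualifying visit precede activation. If half of those returning could gain (assumed), 9 to 16 patients are affected and 11 points becomes 10.7 to 10.5 (power 0.81 to 0.79).

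**The case against.** The strongest reply is that the design sections already place roll-out late. Section 4.1.3 puts it in the analysis phase, 1.3 carries the intervention row to January 2025, and 1.1 lists a 12-month follow-up period. Section 9.1.6 is an optional dissemination clause that sets an earliest point and no date. Read together, these could mean that every 6-month window closes first. That reading is fair, but no passage states it: Phase 3 is undated, the row in 1.3 combines CDS operation with data collection, and 9.1.6 names only the intervention period.

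It can also be said that the analysis is not silent: arm is fixed at the index visit, so later recognition counts as randomized. This stands. The primary analysis needs no change, and what is missing is protection of the contrast or a check on it. It also stands that the return fractions are rough. They apply an all-patient visit rate to patients who needed at least three high BPs in two years, so 15-27% is a working range and not a limit.

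Three stronger readings are tempting and not supported:
- A reader might infer that usual-care clinics were activated in February 2024. The documents do not say whether or when any was.
- A reader might treat all 118 open-window patients as contaminated. Section 8.3 scores those with no follow-up visit at the index visit, so later activation cannot alter their outcome.
- A reader might assume that every window had closed before the March 2025 amendment (9.3). The January 2024 end is only anticipated. If the July 31, 2025 date reflects a longer period, some 12-month windows may have closed later.

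**Conclusion.** The concern holds as a gap in the wording with a limited consequence. Followed literally, 9.1.6 lets usual-care clinics receive the CDS while about one third of usual-care H3 windows are open (about one quarter with a 24-month period). The resulting bias is toward no difference, so it cannot manufacture a positive H3 result. At the planned 17-point difference, power stays at 0.98 or above across the assumed return rates. The loss matters mainly if the true difference is near 11 points, where power falls from 0.83 to between 0.79 and 0.75. The 12-month BP comparison is more exposed, with about two thirds of windows open, but it is exploratory.

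These figures rest on activation immediately at month 18, uniform accrual, equal clinic sizes, the assumed return rates and full uplift for each returning patient. Later activation or accrual that tails off reduces them; faster return raises them. With activation 6 months or more after the period ends, the H3 exposure is zero.

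**What to change.** 1. In 9.1.6 and 4.1.3, state that no usual-care clinic is activated before the last 6-month window closes, or the last 12-month window for the BP comparison.
2. Reconcile the dates in 1.1 (the January 2024 and January 2025 dates and July 31, 2025) with the Phase 2 row in 1.3.
3. State whether and when the CDS was activated at each usual-care clinic. If none was activated before its windows closed, one sentence settles the point.
4. Only if any was activated early, keep the primary endpoint and analysis unchanged and add to 8.4 one H3 sensitivity analysis. Restrict it, in all arms alike, to patients whose full 6-month window ended before one calendar date, the earliest usual-care activation.

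**Cost.** A delay of about 6 months (12 for BP) in an optional roll-out, if it is still ahead; otherwise a few sentences and a record of dates. The sensitivity analysis uses fewer patients. With activation right at month 18 and uniform accrual it keeps 1,060 × 12/18 = 707 (15.7 per clinic, design effect 1 + 14.7 × 0.035 = 1.51), with power 0.74 at 11 points and 0.98 at 17. It is therefore a check and not a substitute for the primary analysis.

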9.2 ABBREVIATIONS AND SPECIAL TERMS

AAP	American Academy of Pediatrics
BP	Blood pressure
BMI	Body mass index
BPA	Best practice advisory
CDS	Clinical decision support
DBP	Diastolic blood pressure
EH	Essentia Health
EHR	Electronic Health Record
HP	HealthPartners
HTN	Hypertension
IRB	Institutional Review Board
LVH	Left ventricular hypertrophy
PI	Principal Investigator
QA	Quality Assurance
SAE	Serious Adverse Event
SBP	Systolic blood pressure
sIRB	Single Institutional Review Board
USPSTF	United States Preventive Services Task Force

11 APPENDIX 1 – ASSESSMENT OF RISK FACTORS

Assessment of Cardiometabolic Disease Risk Factors and Health-Related Social Needs in Pediatric Patients with and without IDD

Background and Rationale:

Cardiometabolic risk in childhood and adolescence is associated with future disease and cardiovascular mortality^{1,2,3}. Although precise definitions and cut-offs may vary, cardiometabolic and cardiovascular disease (CVD) risk in childhood and adolescence can be measured across five domains (blood pressure (BP), lipids, glucose/Hgb A1c, smoking, body mass index (BMI)). Of these, BP and BMI are routinely assessed at all pediatric primary care visits, smoking status may be assessed during adolescent well visits, and lipids and glucose/Hgb A1c may only be assessed in patients with obesity or other risk factors^{4,5,6}.

People with Intellectual and Developmental Disabilities (IDD) have higher rates of cardiometabolic risk factors and cardiovascular disease compared to similar patients without IDD^{7,8}. There is evidence that this risk begins to accumulate in childhood, but there is a lack of data describing the prevalence of CVD risk factors in pediatric patient populations with IDD. In order to learn how to better serve pediatric patients with IDD and their families and prolong length and quality of life for individuals with IDD, better data on risk factors and areas for potential risk modification are needed.

Essentia Health started routinely collecting data on patients' health-related social needs (HRSN) in 2020 in all primary care visits. This includes personal and medical transportation, food scarcity and food insecurity, and financial strain aimed to identify those report any adverse social conditions that can contribute to poor health^{9,10,11}. Prior studies have noted an association between CVD risk and HRSN¹².

The PedsBP clinical decision support (CDS) tool has potential to improve BP measurement, remeasurement and control, as well as raise awareness of CVD risk factors and work up for secondary causes¹³. Assessment of HRSN routinely occurs in primary care clinics and association of HRSN and CVD risk factors is important to describe.

This cross-sectional analysis utilizes the baseline data from patients' PedsBP CDS index visit obtained from web service call data that is gathered at the index visit, as well as historical data prior to the index visit that will be gathered from the EHR.

Aims:

1. In youth 6-17 years of age, describe the assessment of CVD risk factor and HRSN data in the EHR by:
 - a. rural vs urban dwelling
 - b. male vs female sex
 - c. IDD vs non-IDD
2. In youth 6-17 years of age with CVD risk factor and HRSN assessment in the EHR, describe the prevalence of CVD risk factors and HRSN:
 - a. rural vs urban dwelling
 - b. male vs female sex
3. Describe the association of CVD risk factors and HRSN.
4. Determine the prevalence of having one or more- cardiometabolic risk factors among a cohort of pediatric patients 6-17 years receiving care in a large, primarily rural health system with a diagnosis of IDD (as defined by

ICD-10 diagnostic codes for IDD). Compare this prevalence with that of patients of similar age in the health system without IDD diagnosis.

Hypotheses:

1. Comparing study-eligible pediatric patients on the assessment of CVD risk factor and HRSN data:
 - a. Assessment of CVD risk factors and HSRN will be more complete in urban-dwelling than rural-dwelling pediatric patients.
 - b. Assessment of CVD risk factors and HSRN will be more complete in female than male pediatric patients.
 - c. Assessment of CVD risk factors and HSRN will be more complete in patients with IDD than patients without IDD.
2. Comparing study-eligible pediatric patients on the prevalence of CVD risk factors and HRSN:
 - a. Rural pediatric patients will have a higher prevalence of CVD risk factors and HRSN than urban pediatric patients.
 - b. Male pediatric patients will have a higher prevalence of CVD risk factors and HRSN than female pediatric patients.
3. Patients with a higher count of HRSN will be more likely to have any CV risk factors.
4. Among those with at least two documented cardiometabolic risk measures, those with IDD will have increased CVD risk, compared with those with no IDD diagnosis.

Population: All PedsBP study-eligible patients aged 6-17 years on the date of a potential index visit (first visit) at a randomized Essentia Health clinic between August 1, 2022, to July 31, 2023.

Exclusion Criteria: Opted out of use of their data for research prior to performing analyses.

Informed Consent: See Section 9.1.1 above.

Main Measures: A complete list of variables that will be collected can be found in the data dictionary (separate document located in the study file).

Variable	Description	Data Source
Patient Description	Age, sex, race, ethnicity, vitals, labs, medications, diagnoses, encounters	CDS, EHR Clarity
Provider Type and Specialty	Standard categories	EHR Clarity
Tobacco and Marijuana Status	Standard categories	EHR Clarity
Rural-urban commuting area (RUCA)	Ruca, zip code(s)	EHR Clarity
Intellectual and Developmental Disabilities (IDD)	Autism spectrum disorder, intellectual disability, cerebral palsy, genetic conditions, child disintegrative disorder, fetal alcohol syndrome	EHR Clarity
Health-Related Social Needs (HRSN)	Personal transportation, medical transportation, food scarcity, food insecurity, and financial strain	EHR Clarity

Analysis Plan:

Aim 1: Describe the assessment of CVD risk factor and HRSN data in the EHR by urban vs. rural patient dwelling, patient sex, IDD vs. non-IDD status.

The count and percentage of patients having assessment in the EHR will be computed for: a) assessment of information needed to document each individual CVD risk factor in the EHR (e.g., BP measured at the index visit, lipids measured ever, glucose or A1c measured ever, smoking assessed in the past 2 years, BMI recorded in the past 2 years, problem list diagnosis of any CVD risk factor), b) documentation of any HRSN in the EHR. These summaries will be computed for all patients and stratified individually and multiply by patient dwelling (rural, urban), patient sex, patient age group. Differences in assessment of information (0/1) for each assessment will be assessed with logistic regression analysis predicting assessment of information from patient factors used as stratification variables.

The same analysis strategy will be used to describe and test assessment of CVD risk factor information and HRSN for patients with IDD vs. non-IDD.

Aim 2. Describe the prevalence of CVD risk factors and HRSN by urban vs. rural patient dwelling, patient sex.

The prevalence of CVD risk factors will be computed as: a) the prevalence of any risk factor among the five of interest, and b) the prevalence of each individual risk factor. HRSN prevalence will be computed as the presence of any HRSN present. These summaries will be computed for all patients having CVD risk factor assessment (and HRSN assessment) from Aim 1 and stratified individually and multiply by patient dwelling (rural, urban), patient sex, patient age group. Differences in prevalence as defined above will be assessed with logistic regression analysis predicting prevalence from patient factors used as stratification variables. In addition, multiple linear regression will be used to assess the association of count of CVD risk factors with patient factors. Models will include the stratification factors listed above.

Aim 3. Describe the association of CVD risk factors and HRSN.

The association of any CVD risk factor (0/1) with presence of HRSN (0/1) overall and stratified individually and multiply by patient dwelling, patient sex, patient age group will be assessed in contingency table analysis and tested via Pearson and Cochran-Mantel-Haenszel chi-square tests. The association of each CVD risk factor with presence of HRSN (0/1) will be addressed with the same approach.

Multiple linear regression will be used to assess the association of count of CVD risk factors with presence of HRSN (0/1). Models will include the stratification factors listed above. One set of models will exclude any interactions and a second set will include interactions in order to formally test for differences in the association of count of CVD risk factor and HRSN by subgroups (e.g., patient age group).

Aim 4. Describe the prevalence of having one or more CVD risk factors in patients with a diagnosis of IDD vs. no diagnosis.

The prevalence of CVD risk factors will be computed as: a) the prevalence of any risk factor among the five of interest, and b) the prevalence of each individual risk factor. HRSN prevalence will be computed as the presence of any HRSN present. These summaries will be computed for all patients having CVD risk factor assessment (and HRSN assessment) from Aim 1, and multiply stratified by IDD vs. non-IDD and patient age group. Differences in prevalence as defined above will be assessed with logistic regression analysis predicting prevalence from IDD vs. non-IDD and patient factors used as stratification variables. In addition, multiple linear regression will be used to assess the association of count of CVD risk factors with IDD vs. non-IDD and patient factors.

References

1. Jacobs DR, Jr., Woo JG, Sinaiko AR, et al. Childhood Cardiovascular Risk Factors and Adult Cardiovascular Events. *N Engl J Med.* May 19 2022;386(20):1877-1888. doi:10.1056/NEJMoa2109191

6. Hagan, J. F., Shaw, J. S., & Duncan, P. M. (2017). Bright futures: Guidelines for health supervision of infants, children, and adolescents: Pocket guide. American Academy of Pediatrics/Bright Futures, 2017. APA, 7th ed.

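### Appendix 1 hypothesis 3 concerns the number of social needs, but Aim 3 tests only any need versus none, so no planned analysis can show a gradient

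*Combined protocol and SAP*

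**What the plan says.** Everything relevant is in section 11, Appendix 1.

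- **Hypotheses, item 3:** "Patients with a higher count of HRSN will be more likely to have any CV risk factors".
- **Main Measures, HRSN row:** five items are listed, "Personal transportation, medical transportation, food scarcity, food insecurity, and financial strain", so a count from 0 to 5 can be formed from data already being collected.
- **Analysis Plan, Aim 3, contingency tables:** "The association of any CVD risk factor (0/1) with presence of HRSN (0/1) overall and stratified individually and multiply by patient dwelling", sex and age group, tested with Pearson and Cochran-Mantel-Haenszel chi-square tests. Individual risk factors follow: "The association of each CVD risk factor with presence of HRSN (0/1) will be addressed with the same approach".
- **Analysis Plan, Aim 3, regression:** "Multiple linear regression will be used to assess the association of count of CVD risk factors with presence of HRSN (0/1"). A second set of these models adds interactions, in order to "formally test for differences in the association of count of CVD risk factor and HRSN by subgroups".
- **Analysis Plan, Aims 2 and 4:** "HRSN prevalence will be computed as the presence of any HRSN present". Aim 1 records only whether any HRSN documentation exists.

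**The concern.** The hypothesis makes a graded claim: children with more needs are more likely to have a risk factor. The plan compares children with no need and children with at least one. A positive result from that comparison fits a steady rise from one need to five. It fits equally well a single step at the first need with no change after it. The planned analyses cannot separate the two, although the second pattern does not bear out a prediction about higher counts in general.

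Two things are at stake. First, one of the appendix's four numbered hypotheses gets only a partial answer. Second, if the investigators later want the graded answer, they will have to choose the scoring, the covariates and the handling of incomplete screening after seeing the data.

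**Working it through.** **Step 1. Set the hypothesis beside each Aim 3 analysis.**

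| Source in Appendix 1 | HRSN enters as | CVD risk enters as | Can show a gradient over number of needs? |
|---|---|---|---|
| Hypothesis 3 | count | any (0/1) | this is the prediction |
| Aim 3, tables, any risk factor | 0/1 | any (0/1) | no |
| Aim 3, tables, each risk factor | 0/1 | each factor (0/1) | no |
| Aim 3, linear regression | 0/1 | count | no |
| Aim 3, same regression with interactions | not recoded | count | no |

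All three analyses state the 0/1 coding for HRSN. The interaction sentence omits the 0/1 label, but it describes a second set of the same models, and the count in it still belongs to the CVD risk factors. The first row of tables comes closest: it has hypothesis 3's outcome, with the exposure cut at its coarsest point. A Cochran-Mantel-Haenszel test can serve as a trend test when the exposure has ordered scores, but here it is applied to a 0/1 exposure, so there is no order to use.

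**Step 2. Look elsewhere in the appendix.** Aims 1, 2 and 4 use HRSN only as any or none. Analyses that use an HRSN count: 0. The separate data dictionary is cited as a list of variables to be collected, not as an analysis plan.

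**Step 3. Size of the loss if risk is linear in the count.** The documents give no HRSN distribution, sample size or power for Appendix 1, so there is no figure of the plan's own to reproduce. What follows is illustration under assumed distributions.

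Let X be the count (0 to 5), m its mean, v its variance and q = P(X > 0). The covariance of X with the indicator of X > 0 is m(1 − q), and the indicator's variance is q(1 − q). The squared correlation, which approximates the share of information kept, is

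r² = m²(1 − q) / (q·v).

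*Worked case, 80% with no need,* probabilities (.80, .10, .05, .03, .015, .005):
- m = .10 + .10 + .09 + .06 + .025 = 0.375
- E[X²] = .10 + .20 + .27 + .24 + .125 = 0.935
- v = 0.935 − 0.375² = 0.7944
- r² = 0.1406 × 0.80 / (0.20 × 0.7944) = 0.71

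*Worked case, 95% with no need,* probabilities (.95, .04, .008, .002, 0, 0):
- m = .04 + .016 + .006 = 0.062
- E[X²] = .04 + .032 + .018 = 0.090
- v = 0.090 − 0.062² = 0.0862
- r² = 0.003844 × 0.95 / (0.05 × 0.0862) = 0.85

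| Assumed P(X = 0, 1, 2, 3, 4, 5) | r² |
|---|---|
| .70, .15, .08, .04, .02, .01 | 0.67 |
| .80, .10, .05, .03, .015, .005 | 0.71 |
| .90, .06, .025, .01, .004, .001 | 0.75 |
| .80, .16, .03, .008, .002, 0 | 0.79 |
| .90, .08, .015, .004, .001, 0 | 0.81 |
| .95, .04, .008, .002, 0, 0 | 0.85 |

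The share kept runs from about 67% to 85%. It is higher where fewer children have several needs.

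**The case against.** The best defence is that none against one or more is itself a comparison of a lower with a higher count, on exactly the outcome that hypothesis 3 names. A clear null or reversed result would count against the hypothesis, and a positive one would be partly consistent with it. That stands. A reader might infer that hypothesis 3 goes untested, or that the plan can neither support nor refute it. The documents do not support that reading, because the Aim 3 table analysis tests the hypothesis at the coarsest cut.

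A reader might also infer that the count was attached to the wrong variable by mistake. The text does not establish this. The same regression on the count of CVD risk factors is planned for Aims 2 and 4, and the any/none HRSN measure is used in both, so Aim 3 follows the appendix's usual measures. The aim itself, to describe the association, is served by the plan. The one-line hypothesis may be the part that is out of step, and for that reason rewording it is a legitimate remedy.

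A simple count also has weaknesses. It gives equal weight to two transport items and two food items that are likely to overlap, and it needs a rule for incomplete screening. Finally, if the effect is mainly any need against none, dichotomising loses little or nothing. These points bear on the choice of remedy and on the size of the loss. They do not remove the mismatch.

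**Conclusion.** The mismatch is real and rests on the text alone. Hypothesis 3 is stated for a count, every Aim 3 analysis uses 0/1, and no analysis in Appendix 1 uses an HRSN count. The hypothesis is tested only in dichotomised form, and a gradient across the number of needs cannot be shown.

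The 67% to 85% range depends on two assumptions: that risk is linear in the count, and that the HRSN distribution resembles one of those tried. It should not be read as a measured loss or as a known fraction of the sample discarded. The conclusion does not depend on it.

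Severity is minor. Appendix 1 is a cross-sectional analysis added by amendment in December 2023, and hypothesis 3 does not bear on the randomised comparisons or on the primary and secondary outcomes in section 8.

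**What to change.** Either of two edits to Appendix 1 resolves the point.

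1. **Add the matching test (preferred, because it answers the question as posed).** Name as the Aim 3 test of hypothesis 3 a logistic regression of any CVD risk factor (0/1) on HRSN count (0 to 5, as a trend), adjusted for dwelling, sex and age group, in children with HRSN assessed. State how partly answered items are handled; Aim 1 counts any HRSN documentation as assessed, so a child with one item answered would otherwise receive a count based on that item alone. Keep the existing 0/1 and risk-factor-count analyses as supportive.
2. **Reword the hypothesis.** Restate hypothesis 3 in terms of presence of any HRSN, so that it matches the planned table analysis, and make no claim about a gradient.

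The first option costs a few sentences and one extra model on data already collected, using a method the appendix already names for its other binary outcomes. The second costs one line. Either should be settled before the Aim 3 data are analysed.
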